6. TREATMENT PLAN

Treatment will be administered on an outpatient basis. Expected toxicities and potential risks as well as dose modifications for ABT-888 and TMZ are described in Section 7 (Expected Toxicities and Dosing Delays/Dose Modifications). No investigational or commercial agents or therapies other than those described below may be administered with the intent to treat the participant's malignancy.

A summary of the treatment plan is provided in Table 6.1 below.

A summary of on study evaluation is provided in the study calendar in Table 10.1.

In summary, all subjects who sign informed consent, enroll in the study, and meet the pre-treatment requirements will receive study drugs. Subjects will self administer ABT-888, 30mg, every 12 hours PO on days 1-7 of each 28 day cycle. Subjects will self administer TMZ, 150-200mg/m², orally once daily on days 1-5 ONLY of each cycle. The dose of TMZ will be 150mg/m² for CYCLE 1, and will increase to 200mg/m² for CYCLE 2 and higher, per section 6.2.2. The intention is for both drugs to be administered concurrently and ABT-888 and TMZ should begin on the same day. If a delay in dosing of either drug is required for any reason, both drugs should be delayed until the subject is eligible to receive both drugs as scheduled concurrently. If for any reason the subject is permanently taken off either ABT-888 or TMZ, the subject will be off study treatment. Refer to Section 6.2 for details of administration of each agent.

Table 6.1 Treatment Descriptions

*** CYCLE 1 ONLY ***					
Agent	Instructions	Dose	Route	Schedule	Cycle length
ABT-888	Take AM dose at same time as TMZ	30mg q 12 hrs	PO	Days 1-7	28 days
TMZ	Take without food	150mg/m ² QD	PO	Days 1-5	
*** CYCLE 2 and HIGHER ***					
Agent	Instructions	Dose	Route	Schedule	Cycle length
ABT-888	Take AM dose at same time as TMZ	30mg q 12 hrs	PO	Days 1-7	28 days
TMZ	Take without food	200mg/m ² QD	PO	Days 1-5	

6.1. Pre-treatment Criteria

After a patient has been determined to be eligible for this study and has provided signed written informed consent, a pre-study baseline evaluation is required as indicated in [Table 10.1](#) prior to initiation of cycle 1. This evaluation must be completed within 1 week prior to starting therapy, except as indicated (imaging may be up to 4 weeks prior). Confirmation that adequate tissue sample is available to be sent to MGH for correlative studies should be obtained prior to enrollment, but tissue may be sent after enrollment. Inability to confirm tissue, however, is not an exclusion to eligibility nor a cause for delay in dosing if other pre-study criteria are met.

6.2. Agent Administration

6.2.1. ABT-888

Dosing

Total daily dose will be 30mg every 12 hours (unless modified according to dose modification instructions below) given on days 1-7 every 28 days.

ABT-888 will be supplied as 10mg capsules. Subjects will be instructed to take 3 (three) 10mg capsules to achieve the 30mg dose.

Subjects will self-administer the morning and evening doses of ABT-888 orally, approximately 12 hours apart in the same calendar day.

On days when TMZ will also be coadministered (days 1-5), the morning dose of ABT-888 and TMZ can be taken at around the same time, but the study drugs should be taken under fasting conditions to reduce the chance of nausea and vomiting per TMZ label recommendation (no food for at least 1 hour before and after dose; water and regular medications are OK). The evening dose of ABT-888 may be taken with or without food.

The following guidelines shall be used regarding missed doses of ABT-888:

- It is recommended that if a subject misses a scheduled dose of ABT-888 and less than 6 hours have passed since the scheduled dosing time, the dose should be taken immediately.
- It is recommended that if more than 6 hours have passed since the scheduled dosing time, the subject should not take the missed dose of ABT-888, but should wait and take the next regularly scheduled dose.
- If the subject vomits within 15 minutes of taking ABT-888, another dose of ABT-888 will be administered. The dose may only be repeated once.
- If the subject vomits and more than 15 minutes have passed from the time of oral dosing of ABT-888 then no additional doses of ABT-888 will be taken.
- For situations not otherwise clearly described above, the principal investigator or designee will provide appropriate instructions for subjects who miss a dose of study drug.

Criteria to treat

There are no known direct clinically significant toxicities due to ABT-888 monotherapy for which dose dependent modification of ABT-888 are necessary. Criteria to treat will be based on the criteria to treat with TMZ, described in Section 6.2.2.

Documentation of dosing

A record of ABT-888 supplied to each subject must be maintained in the source documents.

Each subject will receive a drug diary (Appendix G) to record the date, time and amount of drug taken.

Subjects will be instructed to return their drug diary and all study drug bottles (empty, partially filled or full) to the study site personnel prior to each cycle and at the Final Visit. The study coordinator will document the bottles returned and the number of capsules per bottle per institutional policy. The bottle(s) will be returned to the Institutional research pharmacy for disposal.

6.2.2. Temozolomide

Dosing

TMZ will be administered orally once a day for 5 consecutive days on days 1-5 and repeated every 28 days.

The dose administered will be determined using the body surface area (BSA) calculated at the beginning of each cycle. The BSA will be calculated from the height obtained at the baseline evaluation and from the weight obtained at the beginning of each cycle. The chart in Appendix B may be used to determine the dose of TMZ based on known BSA. A maximum BSA of 2.5 for TMZ dose calculation will be used for subjects with BSA>2.5.

TMZ dosing will be as follows, shown schematically in Table 6.2:

Cycle 1 Only:

[figure not shown]
The dose for the first cycle of TMZ is 150 mg/m²/day. Blood counts will be monitored day 15 and 22 for cycle 1.

Cycle 2 and higher:

The dose for cycle 2 and higher will be determined as follows:

- If during the first cycle, all clinically significant CTCAE non-hematological toxicity attributable to TMZ observed was Grade ≤ 2 (except for alopecia) and with platelets $\geq 100,000/\text{ul}$ and ANC $\geq 1500/\text{ul}$ then TMZ dose should be escalated to 200 mg/m²/day and this dose should be used as the starting dose for subsequent cycles.
- If treatment after cycle 1 has to be delayed because of ongoing clinically significant non-hematological toxicity of CTCAE grade > 2 , then no escalation is possible. If subject does not meet the criteria for dose escalation then the subject should remain at the 150mg/m²/day dose.
- If during the first cycle the subject experiences platelets $< 50,000/\text{ul}$ and/or ANC $< 1000/\text{ul}$ and/or a clinically significant non-hematologic toxicity $>$ grade 3 then subject should postpone therapy until ANC $> 1500/\text{ul}$ and platelets $>100,000/\text{ul}$ and reduce dose to 100mg/m²/day per dose reduction in Section 7.
- If the dose was not escalated at cycle 2 then the dose should not be escalated in further cycles.

Table 6.2 TMZ Dosing Modification For Cycle 2

The start of the each cycle will be scheduled 28 days \pm 3 days after the last day of the previous cycle.

Capsules of TMZ are available in 5, 20 and 100 mg strengths. The daily dose will be rounded to the nearest 5 mg. However, for patient convenience the dose may be rounded up or down no more than 5% from calculated dose in order to minimize the number of pills per dose. The exact dose administered should be recorded in the CRF. Each daily dose should be given with the least number of capsules. Appendix C may be used to assist in calculating to capsule combinations to achieve the desired dose. Subjects will be instructed to fast for at least one hour before and one hour after administration of TMZ. Water is allowed during the fast period. Subjects should be told to swallow the whole capsules in rapid succession without chewing them. If vomiting occurs during the course of treatment, no re-dosing of the subject with TMZ is allowed before the next scheduled dose. Missed doses will not be made up. For situations not otherwise clearly described above, the principal investigator or designee will provide appropriate instructions for subjects who miss a dose of study drug.

Please see Section 7 for dose modification guidelines.

Criteria to Treat

Prior to each 5-day treatment with TMZ a complete blood count (CBC) must be obtained (within -3 days prior to dosing, except for cycle 1 which may be -7 days). Blood counts will be evaluated again day 15

and 22 for cycle 1 and on day 22 for cycle 2 and higher. Within -3 days prior to first dose of each 5-day TMZ treatment the subject must have an ANC \geq 1500/ μ l and platelet count \geq 100,000/ μ l. On day 1 of each cycle (within -3 days) all clinically significant treatment related non-hematological toxicity grade 3 or 4 (except for alopecia) must have resolved (CTCAE grade \leq 1). If toxicity persists, treatment should be delayed by about one week for up to 3 consecutive weeks. If after 3 weeks of delay all clinically significant treatment related toxicity has still not resolved then subject should be discontinued from study treatment.

Documentation of dosing

A record of TMZ supplied to each subject must be maintained in the source documents.

Each subject will receive a drug diary ([Appendix G](#)) to record the date, time and amount of drug taken.

Subjects will be instructed to return their drug diary and all study drug bottles (empty, partially filled or full) to the study site personnel prior to each cycle and at the Final Visit. The study coordinator will document the bottles returned and the number of capsules per bottle per institutional policy. The bottle(s) will be returned to the Institutional research pharmacy for disposal.

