Clinically significant hematological toxicities should result in TMZ dose reduction or delay. During treatment, CBCs should be monitored and the next cycle of therapy should not be started unless the ANC is $> 1500/\mu\text{L}$ and platelet count is $> 100,000/\mu\text{L}$. For any Grade 3/4 toxicities attributable to TMZ, dose reduction and/or delay guidelines should be followed per Table 7.2.1. Dose reductions in the next cycle should be based on lowest blood counts and worst non-hematologic toxicity observed in the previous cycle. The $75 \text{ mg/m}^2/\text{day}$ dose is the lowest dose of TMZ that is allowed in this study. Subjects must stop TMZ and ABT-888 if they are at the $75 \text{ mg/m}^2/\text{day}$ dose level of TMZ and require an additional dose reduction (per Table 7.2.1) due to toxicities. Temozolomide dose levels to be used for dose reductions are summarized in Table 7.2.2.

For TMZ dosage calculations based on body surface area please refer to Appendix B.

Important:

- If the dose was **reduced or delayed** for toxicity, there will **be no dose re-escalation**.
- Any event of seizure that was clearly attributable to ABT-888 requires discontinuation of ABT-888.

Table 7.2.1 ABT-888 and TMZ Dose Reduction or Delay

	Adverse Event	Dose Reduction
Hematologic Toxicity attributable to TMZ	ANC < 1000/ μ L* and/or Platelets < 50,000/ μ L*	
 1. Hold TMZ and ABT-888. Check CBC weekly until recovery to: ANC > 1500/μL and platelets > 100,000/μL and 2. Reduce TMZ dose by 1 dose level at the next cycle***
	ANC 1000/ μ L* to 1500/ μ L* Platelets 50,000/ μ L* to 100,000/ μ L*	
 1. Hold TMZ and ABT-888. Check CBC weekly until recovery to ANC > 1500/μL and platelets > 100,000/μL and 2. Maintain Current TMZ Dose at the next cycle
Non-hematologic Toxicity attributable to TMZ	Nausea/Vomiting CTC \geq Grade 3 despite optimal antiemetic therapy	
 1. Delay cycle until Grade 1 (or Grade 2 if present at baseline) and 2. Reduce TMZ dose by 1 dose level for the next cycle***
	Fatigue, constipation, anorexia or headaches CTC \geq Grade 3	
	Any other CTC \geq Grade 3 deemed to be clinically significant by PI	
	Adverse Event	Dose Reduction**

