Attributable to ABT-888	Any Grade 3 or 4 toxicity which is not attributable to TMZ or underlying disease	
 1. Delay cycle until Grade 1 (or Grade 2 if present at baseline) and 2. Reduce ABT-888 dose to 20 mg q12 hrs . and 3. Reduce TMZ dose by 1 dose level for the next cycle

* Regardless of attribution.

** There will only be one ABT-888 dose reduction allowed.

*** TMZ dose cannot be reduced below 75 mg/ m^2 /day.

Table 7.2.2 Temozolomide Dose Level Definition Summary

Dose Level	Temozolomide Dose
1	200 mg/ m^2 /day
2	150 mg/ m^2 /day
3	100 mg/ m^2 /day
4	75 mg/ m^2 /day

[figure not shown]

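### After a resolved cycle 1 Grade 3 non-haematological toxicity, Section 6.2.2 and Table 7.2.1 give different cycle 2 temozolomide doses, and no sentence expressly ranks one above the other

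*Combined protocol and SAP*

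**What the plan says.** Section 6.2.2, under the text for cycle 2 and higher, has four bullets, numbered here in order.

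- Bullet 1 raises TMZ to 200 mg/m2/day if "all clinically significant CTCAE non-hematological toxicity attributable to TMZ observed was Grade" 2 or lower (alopecia excepted), platelets are at least 100,000/µl and ANC is at least 1500/µl.
- Bullet 2 bars escalation in one situation: "If treatment after cycle 1 has to be delayed because of ongoing clinically significant non-hematological toxicity of CTCAE grade" above 2. It then adds: "If subject does not meet the criteria for dose escalation then the subject should remain at the" 150 mg/m2/day dose.
- Bullet 3 reduces to 100 mg/m2/day, citing Section 7, for platelets below 50,000/µl, ANC below 1000/µl, "and/or a clinically significant non-hematologic toxicity" above Grade 3. This trigger is not limited by attribution.
- Bullet 4: "If the dose was not escalated at cycle 2 then the dose should not be escalated in further cycles".

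Table 7.2.1 in Section 7.2 sets its thresholds differently. Its non-haematological TMZ rows act at Grade 3 or higher, including any other event of at least "Grade 3 deemed to be clinically significant by PI", and lower TMZ by one level. Its last row, for toxicity attributable to ABT-888, covers "Any Grade 3 or 4 toxicity which is not attributable to TMZ or underlying disease". That row orders ABT-888 down to 20 mg every 12 hours and also: "Reduce TMZ dose by 1 dose level for the next cycle". The text of 7.2 bases reductions on the worst non-haematological toxicity of the previous cycle.

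**The concern.** A prescriber choosing the cycle 2 dose can find two answers for one patient. The plan itself sends that decision to 6.2.2: the Section 6 summary says TMZ rises to 200 mg/m2/day at cycle 2 per that section, and Table 6.1 lists 200 without conditions. Bullet 3 cites Section 7, but bullet 1 does not.

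The ABT-888 case is the easier one to miss. The ABT-888 text in 7.2 states only the ABT-888 cut and points to the table. The TMZ text in 7.2 sends the reader to the table for toxicities attributable to TMZ. The TMZ cut for an ABT-888 toxicity therefore appears in a single table cell.

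What is at stake is the dose given to an individual patient just after a Grade 3 toxicity, and consistent dosing across prescribers in a study that sets out to describe safety.

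**Working it through.** **Inputs.** The cycle 1 dose is 150 mg/m2/day (6.2.2). Table 7.2.2 gives the dose levels: level 1 = 200, level 2 = 150, level 3 = 100, level 4 = 75 mg/m2/day. Daily doses come from Appendix B.

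**The plan's own figure.** One level below 150 (level 2) is 100 (level 3). This matches the 100 stated in bullet 3, so the two sections use the same dose ladder.

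**Does resolution cancel the table's cut?** No. The cut applies at the next cycle, and 7.2 uses the worst toxicity of the previous cycle. Resolution without delay is plausible: ABT-888 ends on day 7 of 28, which leaves 28 − 7 = 21 drug-free days.

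**Rules side by side** for a non-haematological event that has resolved before cycle 2. Adequate counts are platelets ≥100,000 and ANC ≥1500. Low counts are platelets <50,000 or ANC <1000. Doses are in mg/m2/day.

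| Cycle 1 event | Counts | Section 6.2.2 | Table 7.2.1 |
|---|---|---|---|
| (a) Grade 3, TMZ | adequate | 150 (bullet 1 fails, bullet 2 says remain, bullet 3 not met) | 100 |
| (a) Grade 3, TMZ | in between | 150 | 100 |
| (a) Grade 3, TMZ | low | 100 (bullet 3) | 100 |
| (b) Grade 3, ABT-888 only | adequate | 200 (bullet 1) | 100 |
| (b) Grade 3, ABT-888 only | in between, e.g. platelets 80,000 | 150 | 100 |
| (b) Grade 3, ABT-888 only | low | 100 (bullet 3) | 100 |
| Grade 4, ABT-888 only | adequate | 200 by bullet 1, 100 by bullet 3 | 100 |

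The 200-against-100 conflict thus needs four things together: Grade exactly 3, attribution to ABT-888 with TMZ and disease excluded, no delay, and adequate counts. Case (a) needs no unusual attribution.

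**Size.**

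- Case (a): 150/100 = 1.5. At 1.7 m2 this is 255 against 170 mg/day, or × 5 days = 1275 against 850 mg per course.
- Case (b): 200/100 = 2.0. At 1.7 m2 this is 340 against 170 mg/day, or × 5 days = 1700 against 850 mg per course. At the 2.5 m2 cap it is 500 against 250 mg/day.

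**Is there a tie-breaker?** Section 6 says dose modifications are described in Section 7. Section 6.2.2 refers the reader to Section 7 for them. Section 7 opens by saying that delays and modifications follow its recommendations. These make Section 7 the natural authority, but none of them says that it overrides bullet 1. The bar on re-escalation in 7.2 presupposes that a reduction or delay has already been applied, so it does not by itself stop a first escalation.

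**The case against.** The strongest reply is that the plan is adequately clear when read as a whole. Section 7 presents itself as the source for toxicity-driven changes, Section 6 points there twice, and the last table row joins the ABT-888 and TMZ cuts as one instruction. A prescriber who applies the whole row gives 100. Within 6.2.2 itself, a Grade 4 ABT-888 event with good counts literally meets both bullet 1 and bullet 3, and the reduction would plainly prevail. This reply stands as the sensible reading. What it does not supply is an express sentence. It also leaves case (a) open, where bullet 2 positively tells the prescriber to stay at 150.

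A second reply is that bullet 3's threshold may be a slip for Grade 3 or higher. The plan is loose with such signs: the ANC restart threshold is at least 1500 in some places and above 1500 in others. If it is a slip, case (a) disappears. In case (b) bullet 3 would then give 100, although bullet 1 would still be met literally. The documents do not show that it is a slip.

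A third reply concerns rarity, and it largely stands for case (b). Section 6.2.1 says ABT-888 alone has no known direct, clinically significant toxicity that calls for dose-dependent modification. Both drugs are taken together on days 1–5, and TMZ's listed toxicities overlap widely with those reported for ABT-888.

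Finally, the Table 6.2 schematic on the cycle 2 dose is a figure that could not be seen. It may settle the matter or repeat the conflict.

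**Conclusion.** The inconsistency is real but minor. For a resolved Grade 3 non-haematological toxicity, the two sections differ by a factor of 1.5 when TMZ is the attributed cause. They differ by a factor of 2.0 when ABT-888 alone is the cause, counts are adequate and bullet 1 is read alone. This rests on the text as printed and on the unseen schematic not resolving it.

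A reader might infer more, and the documents do not support it:

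- *That the protocol leaves the dose ungoverned, or directs a doubling after toxicity.* It does not. The 200 outcome arises only if the cycle 2 dose is set without consulting Table 7.2.1, and Section 7 is the evident, though unranked, authority.
- *That a rate can be put on these cases.* Phase 1 dose-limiting toxicities (Section 3.3) are a different outcome, with no definition, window or attribution by drug given. Serious vomiting in 3 of 24 phase 1 patients (Section 7.1.1) concerns seriousness and not grade. No frequency is estimated here.
- *That the response-rate design is affected.* The decision rules of 5 of 41 and 7 of 20 do not depend on this point.
- *That Grade 3/4 anaemia or lymphopenia falls in case (b).* Both are listed TMZ toxicities in 7.1.2, and under 12.2.1 laboratory values are adverse events only in certain conditions.

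**What to change.** Make three wording changes in 6.2.2.

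1. In bullet 1, add the condition: *and no toxicity requiring TMZ reduction under Table 7.2.1 occurred in cycle 1*. With this in place, bullet 1's attribution wording need not be widened to name ABT-888.
2. In bullet 3, change the non-haematological trigger to clinically significant toxicity of Grade 3 or higher attributable to TMZ or ABT-888, so that it matches the table.
3. In bullet 2, limit the instruction to remain at 150 to patients to whom bullet 3 does not apply.

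Then check the Table 6.2 schematic against the new text.

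The cost is protocol wording only, with no new tests. Patients with a resolved, treatment-related Grade 3 non-haematological toxicity would receive 100 and not 150, as Table 7.2.1 already directs. At 1.7 m2 that is 255 − 170 = 85 mg/day less, a cut of one third. They could not be escalated later, under bullet 4 and the no-re-escalation rule in 7.2. Adding attribution to bullet 3 also means that a Grade 4 event due to neither drug would no longer trigger it. That fits the statement in 7.2 that interruptions for clearly unrelated events should not force a reduction, but the clinical team should confirm it.

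If the team intends 150 for the TMZ-attributed group, it should instead amend the TMZ rows of Table 7.2.1 for the cycle 2 dose, and keep only the bullet 1 change and the ABT-888 row as it stands.

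### Section 6.2.2 and Table 7.2.1 give different cycle-2 temozolomide doses after some grade 3 non-hematologic events in cycle 1: 150 versus 100, or 200 versus 100 mg/m²/day

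*Combined protocol and SAP*

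**What the plan says.** Section 6.2.2 sets the cycle-2 TMZ dose from what happened in cycle 1, which is given at 150 mg/m²/day. It has three relevant bullets.

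- **Escalation to 200.** Counts must be adequate, and the toxicity condition is that "all clinically significant CTCAE non-hematological toxicity attributable to TMZ observed was Grade" 2 or lower. Only TMZ-attributable events count.
- **No escalation.** "If subject does not meet the criteria for dose escalation then the subject should remain at the 150mg/m²/day dose".
- **Reduction to 100.** The triggers are low counts "and/or a clinically significant non-hematologic toxicity $>$ grade 3 then subject should postpone therapy". This bullet has no attribution limit. It refers to Section 7 for the reduction, and the only recovery it names is that of blood counts.

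Section 7.2 has its own rule: "For any Grade 3/4 toxicities attributable to TMZ, dose reduction and/or delay guidelines should be followed per Table 7.2.1". It adds: "Dose reductions in the next cycle should be based on lowest blood counts and worst non-hematologic toxicity observed in the previous cycle". For TMZ-attributable non-hematologic toxicity, Table 7.2.1 acts at grade 3 or above: "Reduce TMZ dose by 1 dose level for the next cycle". Nausea and vomiting count only despite optimal antiemetic therapy, and events outside the named list count only if the principal investigator judges them clinically significant. A separate row covers grade 3 or 4 events attributed to ABT-888; it lowers ABT-888 and also lowers TMZ by one level.

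**The concern.** Two rules in one protocol assign different doses to the same patient at the same visit. If a site follows Section 6.2.2 alone, a patient may be re-treated at the TMZ dose that produced a grade 3 event, or be escalated by a third where the table reduces by a third.

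The choice carries forward. Section 6.2.2 bars later escalation if there was none at cycle 2, and Section 7.2 bars re-escalation after a toxicity reduction or delay. The cycle-2 dose also fixes how many reductions remain before the mandatory stop below 75 mg/m²/day. The issue is dosing safety and consistency between treating physicians, not the efficacy test.

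**Working it through.** No figure in the plan needs reproducing. The check applies both rules to the same patient.

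**Inputs.** Cycle-1 TMZ is 150 mg/m²/day (Section 6.2.2). The dose levels are 200, 150, 100 and 75 mg/m²/day (Table 7.2.2), so one level below 150 is 100. TMZ is given for 5 days per cycle. Body surface area 1.7 m² is one row of Appendix B, used for illustration.

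**Side by side** (cycle-2 TMZ, mg/m²/day; counts adequate in the first four rows):

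| Finding in cycle 1 | Section 6.2.2 | Table 7.2.1 |
|---|---|---|
| TMZ-attributable non-hematologic, grade 2 or lower | 200 | no reduction |
| TMZ-attributable, clinically significant, exactly grade 3, meets a table trigger | 150 | **100** |
| The same at grade 4 | 100 | 100 |
| ABT-888-attributed non-hematologic, grade 3, resolved in time | 200 | **100** |
| ANC below 1000 or platelets below 50,000 | 100 | 100 |
| Lowest count between those limits and ANC 1500 or platelets 100,000 | 150 | 150 |
| Lowest count exactly ANC 1500 or platelets 100,000 | 200 | hold, then 150 |

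**Case (a), second row.** Grade 3 fails the escalation condition and is not above grade 3, so the default of 150 applies. In Section 7.2 it meets the table trigger and gives 100. Basing the reduction on the worst toxicity of the previous cycle covers the step from cycle 1 to cycle 2, and no text exempts it.

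**Case (b), fourth row.** An event attributed to ABT-888 does not count against escalation, so 6.2.2 gives 200. Resolution in time is a necessary condition, because the second bullet blocks escalation when an ongoing event above grade 2 delays the cycle. The ABT-888 row of the table gives 100. That TMZ step appears only in the table; the ABT-888 text of Section 7.2 mentions only the ABT-888 reduction. If the sign in the third bullet were ≥, Section 6.2.2 would itself give both 200 and 100 here, so this conflict does not depend on the sign.

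**Size.**
- Case (a): (150 − 100)/150 = 33%. At 1.7 m²: 255 versus 170 mg/day; × 5 = 1275 versus 850 mg per course, a difference of 425 mg.
- Case (b): (200 − 100)/200 = 50%. At 1.7 m²: 340 versus 170 mg/day; × 5 = 1700 versus 850 mg per course, a difference of 850 mg.
- Reductions left before the mandatory stop: two from 150 (to 100, then 75), one from 100 (to 75).

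**Recovery before the next cycle.** The treatment criteria in Section 6.2.2 ask for grade 1 or lower. The opening of Section 7.2 adds a baseline exception, and Table 7.2.1 and the ABT-888 text of Section 7.2 allow grade 2 if present at entry. The mismatch therefore lies in Section 6.2.2.

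**The case against.** The strongest reply is that Section 7 plainly governs. The opening of Section 6 sends dose modifications there, Section 7 says its recommendations will be used, and Section 6.2.2 points to it twice: "per dose reduction in Section 7" and "Please see Section 7 for dose modification guidelines". On this view the stay-at-150 sentence only completes the escalation rule. That makes Section 7 the likelier rule. It does not settle the matter: the Section 6 summary also refers the cycle-2 dose to Section 6.2.2, and no sentence ranks the two sections or removes the explicit 150 instruction.

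Second, case (a) turns on one > sign, which could be a ≥ that lost its underline when the PDF was read. The same section renders ≥ correctly elsewhere, but the risk remains, and the Table 6.2 schematic of this rule is not visible. Case (b) is untouched by this.

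Third, the affected group is small. Section 3.3 reports that the commonest grade 3/4 events were thrombocytopenia and neutropenia, and Section 6.2.1 knows of no ABT-888 monotherapy toxicity that calls for dose modification. This stands.

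Several stronger readings are tempting but not supported:

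- *Every grade 3 event is in conflict.* Grade 3 vomiting without optimal antiemetics triggers no reduction in the table's vomiting row and stays at 150 in Section 6.2.2, so the two agree.
- *Patients are re-treated with a grade 3 event still present.* The treatment criteria in Section 6.2.2 require resolution first.
- *A patient with baseline grade 2 toxicity must be discontinued under Section 6.2.2.* That criterion concerns treatment-related toxicity, so a return to baseline can be read as resolution. Discontinuation after 3 weeks of delay is one reading, not the only one.

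**Conclusion.** The conflict is real but narrow. On the visible text the two sections differ by 150 versus 100 mg/m²/day in case (a) and 200 versus 100 in case (b). The hematologic rules agree except at exactly ANC 1500/µL or platelets 100,000/µL, a trivial boundary. The conclusion assumes that the > sign is as printed (case (a) only), that the unseen schematic does not resolve the matter, and that the reduction is counted from the 150 given in cycle 1.

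The documents give no rate for either event, so none is estimated. Serious vomiting in 3 of 24 phase 1 subjects (3/24 = 12.5%, Section 7.1.1) is not a substitute: it counts serious rather than grade 3 events, is not limited to cycle 1, and comes from a dose-ranging study.

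A reader might infer that the efficacy conclusions are at risk. The documents do not support this. The rules of at least 5 of 41 responders, and at least 7 of 20 in the expansion cohort, are binomial cut-offs that do not involve the dose rule, so alpha and power are unchanged. The text should be corrected because the ambiguity concerns safety and the remedy is short.

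**What to change.** 1. In the third bullet of Section 6.2.2, replace the non-hematologic trigger with: any non-hematologic toxicity meeting a Table 7.2.1 reduction trigger (TMZ or ABT-888 row). This keeps the table's antiemetic and clinical-significance qualifiers and the Section 7.2 exemption for events clearly unrelated to study drug. Changing > to ≥ alone would lose the antiemetic qualifier and would not settle case (b).
2. State that this bullet overrides the escalation and stay-at-150 bullets.
3. In the treatment criteria of Section 6.2.2, and for non-hematologic recovery in the third bullet, use the Table 7.2.1 standard: grade 1, or grade 2 if present at baseline.
4. Check that the Table 6.2 schematic matches.

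The cost is a short wording amendment; Table 7.2.1 is unchanged. The few affected patients receive a lower TMZ dose and have one fewer reduction step than from 150. A patient with grade 2 toxicity at baseline may resume at grade 2.

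Two separate housekeeping items could go in the same amendment. Section 6.2.2 counts the start of a cycle from the last day of the previous one, an evident slip for day 1. It also lists the day-15 blood count for cycle 1 only, whereas Table 10.1 lists it for cycles 1 and 2.
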